## 10.5 Utility Evaluation

Utility evaluation is the frequency and duration of CGM use and use of the closed loop system at home.

- Percentage of time of closed loop operation
- Percentage of time of CGM availability

## 10.6 Human Factors

Human Factors evaluation will assess the emotional and behavioural characteristics of participating subjects and family members and their response to the closed-loop system and clinical trial using validated surveys, sleep assessment and semi-structured interviews.

## 10.7 Health Economics

Health economic analysis will be performed contrasting the artificial pancreas (closed-loop) and sensor augmented pump therapy using a health economic simulation model: the IMS IQ VIA Core Diabetes Model (CDM). Long-term outcomes derived from the simulation will include total direct costs, life expectancy, quality-adjusted life expectancy and time to onset of complications. Incremental costs versus incremental effectiveness (quality-adjusted life years [QALYs]) for closed-loop vs sensor augmented pump therapy will be compared.

## 10.8 Extension Phase Outcomes (UK sites only)

### 10.8.1 Primary endpoint and key endpoints

The primary endpoint is the difference in time spent with sensor glucose levels between 3.9 to 10.0 mmol/l (70 to 180 mg/dl) during the 18 months extension phase, as compared to sensor augmented pump therapy during the primary phase.

### 10.8.2 Secondary endpoints

Secondary endpoints include:

- Time spent above target glucose (10.0 mmol/l) (180 mg/dl)
- HbA1c
- Average of glucose levels
- Time spent below target glucose (3.9 mmol/l) (70 mg/dl)
- Standard deviation, and coefficient of variation of glucose levels
- Time with glucose levels <3.0 mmol/l (54 mg/dl)

- Time with glucose levels in significant hyperglycaemia (glucose levels  $> 16.7$  mmol/l) (300 mg/dl)
- BMI SDS
- Total, basal, and bolus insulin dose

Endpoints regarding glucose levels will be based on sensor glucose data.

Safety and utility evaluations will be assessed as described above. Human factor evaluation will assess the emotional and behavioural characteristics of participating subjects and family members and their response to the closed loop system and extension phase using validated surveys.

## **11 Assessment and Reporting of Adverse Events**

### **11.1 Definitions**

#### **11.1.1 Reportable Adverse Events**

A reportable Adverse Event is any untoward medical occurrence that meets criteria for a serious adverse event. Device deficiencies that could have led to a serious adverse device effect will also be reported.

#### **11.1.2 Adverse Events**

An adverse event (AE) is any untoward medical occurrence, unintended disease or injury, or untoward clinical signs (including abnormal laboratory findings) in a subject who has received an investigational device, whether or not related to the investigational medical device. This definition includes events related to the device under investigation or the comparator or to the study procedures. For users or other persons, this definition is restricted to events related to the investigational device.

The following anticipated adverse events will not be recorded:

- Non clinically significant skin reactions as judged by investigator
- Pre-existing medical conditions
- New illnesses or conditions not requiring concomitant medication or medical intervention/procedures
- Non severe hypoglycaemia
- Hyperglycaemia without significant ketonaemia ( $>0.6$  mmol/l)

#### **11.1.3 Adverse Device Effect**

An Adverse Device Effect (ADE) is an adverse event related to the use of an investigational medical device. This includes adverse events resulting from insufficient or inadequate instructions for use, deployment, implantation, installation, or operation,

or any malfunction of the investigational medical device. This definition also includes any event resulting from use error or from intentional misuse of the device under investigation.

The following anticipated adverse device effects will not be recorded:

- Non clinically significant skin reactions due to sensor or infusion set use as judged by investigator

#### **11.1.4 Serious Adverse Event**

A serious adverse event (SAE) is an adverse event that:

- led to a death
- led to a serious deterioration in the health of the subject, that either resulted in:
  - a life threatening illness or injury
  - a permanent impairment of a body structure or function
  - in-patient hospitalisation or prolonged hospitalisation
  - medical or surgical intervention to prevent life-threatening illness or injury or permanent impairment to a body structure or a body function
- led to foetal distress, foetal death or a congenital abnormality or birth defect

A planned hospitalisation for pre-existing condition, or a procedure required by the study protocol, without a serious deterioration in health, is not considered to be a serious adverse event.

More than one of the above criteria can be applicable to one event. Life-threatening in the definition of a serious adverse event or serious adverse reaction refers to an event in which the subject was at risk of death at the time of the event; it does not refer to an event which hypothetically might have caused death if it were more severe. Medical judgement should be exercised in deciding whether an adverse event or reaction is serious in other situations.

Important adverse events or reactions that are not immediately life-threatening or do not result in death or hospitalisation but may jeopardise the subject or may require intervention to prevent one of the other outcomes listed in the definition above, should also be considered serious.

The following serious adverse events, should they occur, will be classified as anticipated:

- Severe hypoglycaemia
- DKA

### **11.1.5 Serious Adverse Device Effect**

A Serious Adverse Device Effect (SADE) is an adverse device effect that has resulted in any of the consequences characteristic of a serious adverse event.

### **11.1.6 Unanticipated Serious Adverse Device Effect**

An Unanticipated Serious Adverse Device Effect (USADE) is a serious adverse device effect which by its nature, incidence, severity or outcome has not been identified in the current version of the protocol.

This includes unanticipated procedure related serious adverse events; that is, serious adverse events occurring during the study procedure that are unrelated to any malfunction or misuse of the investigational medical device.

An Anticipated Serious Adverse Device Effect (ASADE) is a serious adverse device effect which by its nature, incidence, severity or outcome has been identified in the protocol.

### **11.1.7 Device Deficiencies**

A device deficiency is an inadequacy of a medical device with respect to its identity, quality, durability, reliability, safety or performance. A device deficiency may lead to an Adverse Device Effect or Serious Adverse Device Effect. The following anticipated device deficiencies and device-related issues will not be recorded:

- Infusion set occlusion/leakage not leading to ketonaemia
- Sensor failure due to miscalibration/detachment
- Premature interruption of sensor-life
- Battery lifespan deficiency due to inadequate charging or extensive wireless communication
- Control algorithm device error messages not needing system replacement
- Intermittent device communication failure not leading to system replacement

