#### **11.2.6 Recording and Reporting of Device Deficiencies**

All device deficiencies will be documented throughout the study. The investigator at each site will be responsible for managing all device deficiencies and determine and document in writing whether they could have led to a serious adverse device effect.

All device deficiencies that might have led to a serious adverse device effect(s) if: suitable action had not been taken, intervention had not been made, or if circumstances had been less fortunate, must be reported to the Sponsor as for SAEs/SADEs.

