### **11.3.7 Risk Analysis and Residual Risk Associated with the Investigational Device**

After in-depth analysis and consideration of all the potential hazards in relation to use of the FlorenceX system in the home environment, it is concluded that the FlorenceX system is safe, if used as intended.

Risk Assessment of the FlorenceX system has been carried out in accordance with ISO 14971:2012. A preliminary Hazard Determination has been carried out including consideration of the questions in Annex C of ISO 14971:2012.

One hazard 'Hazard S7: Incorrect Calibration of Blood Glucose Sensor due to error of reading resulting in overestimation of blood glucose' is the only hazard identified that could not be reduced to an acceptable risk level, post mitigation. Our in-detail risk/benefit assessment concluded that the benefits of the system outweigh the risk with respect to this specific hazard.

As per our risk management process, further risk analysis shall be undertaken post production and release as to ensure any issues raised are acted upon to ensure the FlorenceX system continues to improve and develop.

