### **12.1.2 Blood Glucose Meter Data**

The blood glucose meter will be downloaded periodically during the whole duration of the study.

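### The not-recorded list in protocol 11.1.7 can be read to cover the sponsor's one unreduced hazard (sensor miscalibration with over-reading), conflicts with 11.2.6, and no count of device deficiencies is planned.

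*Combined protocol and SAP*

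**What the plan says.** Protocol 11.1.7 defines a device deficiency and then sets a rule, "The following anticipated device deficiencies and device-related issues will not be recorded", followed by six items. The second is "Sensor failure due to miscalibration/detachment".

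Protocol 11.2.6 states, without exception, "All device deficiencies will be documented throughout the study". The investigator must determine and document in writing whether each could have led to a SADE, and those that might have done so go to the sponsor on the same footing as serious adverse events. Protocol 11.1.1 also makes such near-miss deficiencies reportable.

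Protocol 11.3.7 describes Hazard S7 as "Incorrect Calibration of Blood Glucose Sensor due to error of reading resulting in overestimation of blood glucose" and says that it "is the only hazard identified that could not be reduced to an acceptable risk level, post mitigation". The same section records that a detailed risk/benefit assessment found the benefits to outweigh this hazard, and it commits to further risk analysis.

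Among adverse events, protocol 11.1.2 excludes "Non severe hypoglycaemia" from recording, and 11.2.3 repeats the exclusion. Severe hypoglycaemia always receives a serious adverse event form.

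**The concern.** The list of problems that need no record contains an item close in substance to the one hazard that the sponsor could not mitigate fully. If a site applies the list as written, it keeps no record of a miscalibrated sensor and so has nothing on which to base the written SADE judgement that 11.2.6 requires. At stake is whether the trial can tell its DSMB, its sponsor and later readers how often this hazard arose in children aged 1 to 7, and whether the further risk analysis promised in 11.3.7 will have trial data to work from.

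**Working it through.** No arithmetic applies. The plan gives no figure for how often sensors are miscalibrated or by how much they over-read. The check is to set the passages side by side.

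1. **Is the hazard live in this trial?** Yes. CGM training (9.3) covers how to calibrate, 13.3 has the sensor calibrated to the manufacturer's instructions, and 13.5 allows meter readings to be used for this.

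2. **Is the exclusion limited by consequence?** No. Three of the six items in 11.1.7 are: "Infusion set occlusion/leakage not leading to ketonaemia", and the items on algorithm error messages and communication failures, which are excluded only where the system does not need replacing. The miscalibration item has no such limit.

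3. **Does the item cover S7?** In part. The item speaks of sensor failure, whereas S7 is a wrong calibration that makes the sensor read too high, possibly while it keeps running. However, 11.1.7 defines a deficiency to include inadequate reliability, safety or performance, and the item names miscalibration as a cause. A site could reasonably apply the exclusion to S7, and another could reasonably not.

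4. **Which rule prevails?** The text does not say. 11.2.6 makes no reference to the 11.1.7 list, and 11.1.7 makes no exception for near-misses.

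5. **Do other routes record the event?** Severe hypoglycaemia is captured. Near-misses are captured if 11.1.1 and 11.2.6 override the list. The monthly contacts (9.9) and the three-monthly extension contacts (9.14.1) record device deficiencies, but what counts as recordable there still depends on 11.1.7. Non-severe hypoglycaemia is not treated as an adverse event, so a miscalibration with only that result leaves no adverse event record.

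6. **Is a count planned?** No. Protocol 14.5 and SAP 8.3 tabulate ketoacidosis, severe hypoglycaemia, adverse events and serious adverse events. SAP 8.2 lists severe hypoglycaemia, ketoacidosis and other reportable adverse events, and the definition in SAP 8.1 does not mention device deficiencies. The DSMB data list in SAP 11 does not name deficiencies either. It includes reportable adverse events, a heading under which protocol 11.1.1 places near-misses, so a near-miss might reach the DSMB that way; other calibration-related deficiencies would not.

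7. **Could the meter data fill the gap?** Protocol 12.1.2 says "The blood glucose meter will be downloaded periodically during the whole duration of the study". Neither the protocol nor the SAP plans a comparison with the sensor.

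**The case against.** The strongest reply is that the protocol already has a safety net. Sensor failure, paired with detachment and followed by early loss of sensor life, reads naturally as loss of a working sensor and not as a running sensor that over-reads. Near-misses are reportable under two sections, severe hypoglycaemia is always captured, and contacts in both arms ask about device deficiencies. Families are trained and assessed on sensor use, and the sponsor has weighed this hazard and accepted it.

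Much of this stands. A reader might infer that S7 becomes visible only once it causes severe hypoglycaemia, or that its recorded count must be zero. The documents do not support either reading: both assume that 11.1.7 overrides 11.1.1 and 11.2.6, which is the point left open.

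A reader might also infer that over-reading biases the sensor-based hypoglycaemia endpoints or the comparison between arms. An over-reading sensor would understate low glucose while it lasts, but the documents give neither the frequency nor the size of over-reading. Both arms use the same CGM, and SAP 4.1 pools all readings over up to 112 days per period. No bias of any stated size can be claimed.

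What the reply does not remove is the unresolved conflict between the recording rules and the absence of any planned count.

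**Conclusion.** The point holds as a conflict in the safety-recording rules. Calibration errors with over-reading that do not end in severe hypoglycaemia may go unrecorded at some sites, and so may be unavailable for the SADE judgement. Even if 11.2.6 is taken to prevail, no tabulation is planned. This rests on two assumptions: that a site could read the exclusion as reaching S7, and that the order of precedence is not settled in these documents. The number of events affected cannot be estimated from them. The primary endpoint analysis and the sample size are unaffected. It is a cheap improvement worth making, not evidence that the hazard was ignored or that the trial's results are distorted.

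**What to change.** - In protocol 11.1.7, remove miscalibration from the not-recorded item and leave detachment. At the least, exempt known miscalibration with over-reading. State that 11.1.1 and 11.2.6 then apply, so that each such event is documented and judged for SADE potential.
- In protocol 14.5 and SAP section 8, add calibration-related device deficiencies to the safety listing, with counts by arm for the primary phase and separately for the extension phase. Add the same item to the DSMB data in SAP section 11.

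The cost is a short entry per event, one listing and somewhat more site recording. The SAP is at version 3.0, with initial analyses marked as completed, so the recording change can help only prospectively, in what remains of the extension phase (expected to complete in October 2022). It cannot recover primary-phase events that were not logged, and the primary-phase counts should carry that caveat.

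A table of paired meter and sensor values from the existing downloads is optional, descriptive and post hoc. It would not be a count of S7: it mixes miscalibration with general sensor error, meter error and timing differences, and a meter value used to calibrate the sensor is not an independent reference.

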### **11.1.8 Adverse Event Intensity**

Intensity	Definition
Mild	Patient is aware of signs and symptoms but they are easily tolerated
Moderate	Signs / symptoms cause sufficient discomfort to interfere with usual activities

Severe	Patient is incapable of working or performing usual activities
--------	--

NB. The term “severe” is often used to describe the intensity (severity) of a specific event. This is not the same as ‘serious’, which is based on patient/event outcome or action criteria (see definition 11.1.4). For example, itching for several days may be rated as severe, but may not be clinically serious.

### 11.1.9 Adverse Event Causality

Intensity	Definition
Not assessable	A report suggesting an adverse event, which cannot be judged because information is insufficient or contradictory, and which cannot be supplemented or verified.
Unlikely	A clinical event, including laboratory test abnormality, with a temporal relationship, which makes a causal relationship improbable, and in which other drugs/treatments, chemicals or underlying disease(s) provide plausible explanations.
Possible	A clinical event, including laboratory test abnormality, with a reasonable time sequence to administration of the treatment/use of investigational treatment/device, but which also could be explained by concomitant diseases or other drugs/treatments or chemicals.
Probable	A clinical event, including laboratory test abnormality, with a reasonable time sequence to administration of the treatment/use of medical method/device, unlikely to be attributable to concomitant disease(s) or other drugs/treatments or chemicals, and which follows a clinically reasonable response on withdrawal (dechallenge). Rechallenge information is not required to fulfil this definition.
Definite/certain	A clinical event, including laboratory test abnormality, occurring in a plausible time relationship to study treatment/use of medical method/device and which cannot be explained by concomitant disease(s), other drugs/treatments or chemicals. The response to withdrawal of the treatment (dechallenge) should be clinically

	plausible. The event must be unambiguous, either pharmacologically or as phenomenon, using satisfactory rechallenge procedures if necessary.
--	--

(Reference: WHO-UMC Causality Categories)

## 11.2 Recording and Reporting of Adverse Events, Serious Adverse Events and Device Deficiencies

### 11.2.1 Monitoring Period of Adverse Events

The period during which adverse events will be reported is defined as the period from the beginning of the study (obtaining informed consent) until 3 weeks after the end of the study participation. Adverse events that continue after the subject's discontinuation or completion of the study will be followed until their medical outcome is determined or until no further change in the condition is expected. The follow up of AEs may therefore extend after the end of the clinical investigation; however no new AEs will be reported after the trial reporting period.

### 11.2.2 Recording and Reporting of Adverse Events

Throughout the course of the study, all efforts will be made to remain alert to possible adverse events or untoward findings. The first concern will be the safety of the subject, and appropriate medical intervention will be taken. The investigator will elicit reports of adverse events from the subject at each visit and complete adverse event forms. All AEs, including those the subject/guardian reports spontaneously, those the investigators observe, and those the subject/guardian reports in response to questions will be recorded on paper or electronic AE forms at each site within seven days of discovering the event.

The study investigator will assess the relationship of any adverse event to be device-related or unrelated by determining if there is a reasonable possibility that the adverse event may have been caused by the study device or study procedures. The individual investigator at each site will be responsible for managing all adverse events according to local protocols, and decide if reporting is required.

### 11.2.3 Severe Hypoglycaemia

In line with current ISPAD consensus guidelines (59), hypoglycaemic events will be considered severe if the event requires assistance of another person due to altered consciousness to actively administer carbohydrate, glucagon, or other resuscitative actions. This means that the subject is impaired cognitively to the point that he/she is

unable to treat him- or herself, is unable to verbalize his or her needs, is incoherent, disoriented, and/or combative, or experiences seizure or coma. If plasma glucose measurements are not available during such an event, neurological recovery attributable to the restoration of plasma glucose to normal is considered sufficient evidence that the event was induced by a low plasma glucose concentration.

Severe hypoglycaemia will be regarded as a foreseeable serious adverse event and a serious adverse event form will be completed. Non-severe hypoglycaemia will not be reported or considered an adverse event.

#### **11.2.4 Diabetic Ketoacidosis**

Biochemical criteria for the diagnosis of ***diabetic ketoacidosis (DKA)*** are defined as per current ISPAD consensus guidelines (60):

- hyperglycaemia (blood glucose >200 mg/dl or >11 mmol/l)
- with either low pH (<7.3) or low serum bicarbonate (<15 mmol/l)
- and ketonemia or ketonuria

DKA will be regarded as a foreseeable serious adverse event and a serious adverse event form will be completed.

#### **11.2.5 Reporting of Serious Adverse Events and Serious Adverse Device Effects**

When reporting adverse events, all pertinent data protection legislation must be adhered to.

The serious adverse event report should contain the following information\*:

1. Study identifier (EudraCT number if applicable)
2. Participant's unique study number
3. Date of birth
4. Event description
5. Start date of event
6. Laboratory tests used and medical interventions used to treat the SAE
7. Planned actions relating to the event, including whether the study device was discontinued
8. Statement on the patient's current state of health
9. Reason for seriousness (i.e. death, life threatening, hospitalisation, disability/incapacity or other)

10. Evaluation of causality (including grade of relatedness) with the following (more than one may apply):

- a. the investigational treatment/medical device
- b. the clinical study/a study specific procedure
- c. other: e. g. concomitant treatment, underlying disease

11. Reporter's name, date and signature

\*In the case of incomplete information at the time of initial reporting, all appropriate information should be provided as soon as this becomes available.

The relationship of the SAE to the investigational treatment / medical device should be assessed by the investigator at site, as should the anticipated or unanticipated nature of any SAEs and SADEs.

All SAEs whether or not deemed investigational method/device related and whether anticipated or unanticipated must be reported to the Sponsor by email or fax within 24 hours (one working day) of the Investigator learning of its occurrence.

SAEs should be reported to:

[name]

Cambridge University Hospitals

NHS Foundation Trust

[name]

[name]

[contact]

[contact]

E-mail: [[contact]](mailto:[contact]).

A written report must follow within five working days and is to include a full description of the event and sequelae, in the format detailed on the Serious Adverse Event reporting form. If applicable, the Sponsor will notify the competent authority of all Serious Adverse Events in line with pertinent legal requirements.

The Investigator will notify the Research Ethics Committee (REC) in UK of all Serious Adverse Events in line with pertinent legal requirements. The Investigator will inform the Sponsor about all reports sent to the reporting organisation including follow-up information and answers by the reporting organisation. The local investigator is responsible for informing other site principal investigators and the CI of all SAEs.

The respective national regulatory authority (e.g. MHRA) will be notified of all SAEs as soon as possible within ten days of the event occurring during the study. The main REC will be notified of all unexpected and related SAEs within 15 days of the occurrence of the event.

